7.3 Subject Population for Analysis

The study will be conducted using a modified intent-to-treat approach in which all randomized subjects who have received at least one dose of study medication and provided at least 10 days of data on drinking after initiating treatment will be used in the efficacy analyses. All randomized subjects who received at least one dose of study medication will comprise the safety population.

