3.2 Primary Study Endpoints

3.2.1 To examine the moderating effects of the GRIK1 SNP rs2832407 on the response to topiramate: The primary outcome measure will be the frequency of HDDs (≥ 5 standard drinks in a day for men and ≥ 4 in a day for women). We chose this outcome because it is a sensitive, clinically relevant measure in alcohol treatment trials (Falk, Wang et al. 2010). Subjects will be followed irrespective of whether they continue to receive treatment, so that the analysis of all outcomes will be based on all of the data available for all randomized subjects. Drinking data for this aim will come from the TLFB (see section 6.10 below).

3.2.2 To examine the relations among daily process measures, medication use, and drinking level: We will use multilevel models to evaluate the associations of alcohol expectancies and self-efficacy (confidence in resisting drinking and heavy drinking) with daily drinking and how these associations vary as a function of medication group and rs2832407 genotype. Similar to Kranzler, Armeli et al. (2013), we will focus on predicting nighttime drinking (i.e., drinks consumed after the early evening report), but here we will use alcohol-related expectancies reported during the early evening in the daily survey. Nighttime drinking levels will be determined by subtracting the number of drinks consumed during the current day from the total number of drinks consumed for that day (reported the following day).

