4.4.2 Data Collection and Follow-up for Withdrawn Subjects

For subjects that leave treatment prematurely, the study nurse or research coordinator will complete the Early Termination Form, indicating the subject's level of functioning at termination. The form is used to identify the reasons for early termination (e.g., symptomatic failure, adverse effects) and other relevant circumstances. Additionally, we will make a strong effort (via phone calls and alternative contact information) to obtain follow-up information on all subjects who are prematurely withdrawn from the project. We will invite subjects to return to the clinic for assessment at the time of their discontinuation from treatment and again at the scheduled end of treatment, as well as all post-treatment follow-up visits. The following efforts will be made to contact subjects who discontinue treatment prior to the twelfth week: 2 telephone calls by the research coordinator or technician resulting in contact (either with the subject or by leaving a message on voicemail or a person answering the subject's telephone, followed by 2 telephone calls by a study physician, followed by a letter. Only if all of these efforts are unsuccessful in obtaining follow-up information (either during an in-person visit or a telephone interview), the subject will be considered to be lost to follow-up.

5 Study Drug

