Subjects will receive the first counseling session and study medication (topiramate or placebo) during the **first treatment session** scheduled on the same day as the baseline assessment (after all assessments have been completed). At this visit, the subject will also meet with the physician. At this (and every) visit, the study nurse experienced in the use of Medical Management in alcohol pharmacotherapy trials will use the method to counsel the subject. This provides a basic clinical intervention that was designed to be used in conjunction with prescribed medication, and to be easily implemented by medically trained practitioners in non-specialty settings. The treatment will support subjects’ efforts to stop or reduce their drinking, with the study nurse making direct recommendations for reducing drinking to sensible levels.

The first counseling session (which will last approximately 30 minutes) will consist of a review of the results of the initial evaluation, identifying any concerns the subject may have. The subject is then provided with a rationale and information about pharmacotherapy and the importance of adherence. Subsequent treatment sessions (approximately 20 minutes) will be conducted at each treatment visit. During these sessions, the study nurse will obtain the subjects’ vital signs and weight, ask about medication side effects and concurrent medications, perform a brief assessment of the subjects’ drinking and medication adherence, and in some cases, make recommendations on strategies for the subject to follow until the next visit. Men will be advised to consume no more than 3 standard drinks per day and 12 standard drinks per week and women will be advised to consume no more than 2 drinks per day and 8 drinks per week. Because subjects will not be physically dependent on alcohol, reduction of heavy drinking is a safe and ethical goal.

CONFIDENTIAL

The physician will meet with the subject at the beginning of treatment and discuss clinical management with the study staff weekly. The physician will evaluate the subject for any severe or persistent adverse effects.

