6.5 Visit 10 (Week 13; Endpoint Visit)

At the end of treatment, week 13 (+/- 4 days) we will repeat the research assessments and will query the subject as to his or her belief regarding their treatment condition using the Medication Questionnaire (MED-Q). Blood samples for measurement of serum GGTP and %dCDT will be obtained to assess the validity of self-reported drinking. Subjects will be asked not to drink before coming to the scheduled visits. Subjects will be asked to complete a breathalyzer test. If a subject's breath alcohol concentration is $\geq 0.02\%$, an investigator will evaluate whether the subject is too impaired to complete the study assessments. The study visit may be completed at the discretion of the investigator. If the subject is deemed to be unable to complete assessments, the investigator may ask the subject to wait until his or her blood alcohol level decreases or if that is not feasible to return the next day after having consumed no alcohol. Prior to discharge from the TRC, a clinician will assess the subject to ensure that it is safe for the subject to leave. Study staff will complete the following assessments with all subjects (the exception being that only for women of childbearing potential, will study staff obtain a urine sample for a pregnancy test). Subjects who are suitable for assessment will then complete questionnaires and be interviewed by the study nurse.

All subjects will be asked to complete an end-of-treatment evaluation and to complete all scheduled assessments to facilitate intent-to-treat (ITT) analyses. All subjects will be informed of these procedures prior to study enrollment. Subjects will be compensated \$50 for completing the end-of-treatment visit. Subjects who decide to terminate the study prior to visit 10 will also receive payment upon completion of the end-of-treatment procedures and 3- & 6-month follow-up visits. For subjects who withdraw early and do not wish to continue with study visits/procedures, all end-of-treatment procedures will be administered at the time of withdrawal. These subjects will also be asked to undergo in-person or telephone follow-up at the end-of-treatment for collection of the remaining treatment-phase Timeline Follow-back data.

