The fixed effects for the primary models will include binary factors for intervention group (Topiramate/ Placebo) and *GRIK1* genotype (CC or AA/AC), and their interaction, with covariates for linear and quadratic time trends and further terms for group by time, genotype by time, etc., as appropriate for model fit. The random effects will include a random intercept and, if necessary, residual autocorrelations, random slopes, or other specifications will be used (Molenberghs, Verbeke et al. 2005, McCulloch, Searle et al. 2008). Although the primary contrasts will concentrate on the final six weeks, these models utilize all available data from all subjects, so the analyses follow the intent-to-treat principle. If the polynomial time trends described above do not capture the range of individual trajectories observed in the trial, then more flexible non-linear time trends can also be fitted. Additional covariates can also be included in the models, allowing for sensitivity analyses for effects of covariate imbalances, and to examine moderation effects (see below) and group by goal of treatment (reduced drinking or abstinence) interactions. For example, we will also include the proportion of European ancestry as a covariate, to adjust for admixture. Here, AIMs genotype data will be used to calculate ancestry proportions using a principal components method implemented in EIGENSTRAT (Price, Patterson et al. 2006) or PLINK (Purcell, Neale et al. 2007), and the proportion will be included in the model as a covariate. The models can also be extended to allow for zero inflation, where weekly patterns of abstinence may yield more zero counts of heavy drinking days than can be accommodated by a Poisson model.

To examine the relations among daily process measures of expectancies, medication use, and drinking level (Specific Aim 2.)

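### Section 7.3 excludes randomised subjects with no dose or fewer than 10 days of drinking data, contradicting the all-randomised promise in 3.2.1 and the intent-to-treat statement in 7.2

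*Combined protocol and SAP*

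**What the plan says.** Three places in the combined protocol and SAP describe who is analysed for efficacy.

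- **Section 7.3** (Subject Population for Analysis): "The study will be conducted using a modified intent-to-treat approach". To enter, a randomised subject must have had at least one dose and have "provided at least 10 days of data on drinking after initiating treatment will be used in the efficacy analyses".
- **Section 3.2.1** (Primary Study Endpoints): "Subjects will be followed irrespective of whether they continue to receive treatment", with the stated purpose that "the analysis of all outcomes will be based on all of the data available for all randomized subjects".
- **Section 7.2** (Statistical Methods, Specific Aim 1), on the primary models: "these models utilize all available data from all subjects, so the analyses follow the intent-to-treat principle".

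Data collection is built for the wider set. Section 4.4.2 promises a strong effort "to obtain follow-up information on all subjects who are prematurely withdrawn from the project". Section 6.5 asks early withdrawals for "in-person or telephone follow-up at the end-of-treatment for collection of the remaining treatment-phase Timeline Follow-back data", and says that completing the assessments is meant to support ITT analyses, though it defines no analysis set. No section says which statement governs or plans an all-randomised sensitivity analysis.

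**The concern.** A randomised subject with 1 to 9 days of drinking data has available data. So does a subject who was never dosed but was followed. Sections 3.2.1 and 7.2 take both in; Section 7.3 leaves both out. The two conditions in 7.3 are met or failed after randomisation, so the set analysed is no longer the set randomised, and the protection that 7.2 claims under the name of intent-to-treat does not strictly apply.

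The primary test is the medication by genotype interaction, with about 50 subjects per cell. If exclusions fell in one cell only, the whole shift in that cell's mean would pass into the interaction contrast. Equal shifts in all four cells would cancel.

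**Working it through.** **1. The sections side by side**

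| Randomised subject | 3.2.1 and 7.2 | 7.3 |
|---|---|---|
| Dosed, 10 or more days of data | in | in |
| Dosed, 1 to 9 days of data | in | out |
| Never dosed, followed with TLFB | in | out |
| No post-randomisation drinking data | adds nothing | out |

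The conflict is confined to the second and third rows.

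**2. The plan's own figures (Section 7.1)**

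200 randomised in four cells gives 50 per cell; 0.94 × 50 = 47, and 4 × 47 = 188, as stated. The 3 per cell lost by week 6 are planned data loss, not subjects without data. Some may have several weeks of TLFB and would pass the 10-day rule.

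The stated power is 81%, for a contrast of 0.93 − 0.27 = 0.66, correlation 0.35 and six weeks. The variance factor is (1 + 5 × 0.35)/6 = 0.4583, and SE = √(4 × 0.4583/47) = 0.1975 SD. The plain formula gives 91.7% (91.1% with the 6% attrition). It comes to 80.7% if the effect is diluted from 0.90 to 0.81 over weeks 7-12 for the stated treatment discontinuation; that dilution is an assumption. The point does not dispute the 81%.

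**3. Illustration of size**

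The documents give neither the number excluded nor their drinking. Assume k = 1 to 3 excluded subjects in one cell of 50, each differing from the rest by a constant g = 1 or 3 heavy drinking days (HDD) per week. Approximate the count model by a linear random-intercept model fitted by generalised least squares: 12 weekly values, linear and quadratic time, correlation 0.35. The table gives the shift in that cell's fitted weeks 7-12 mean, included versus excluded, in HDD/week.

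| Data held by the excluded subjects | k=1, g=1 | k=3, g=1 | k=1, g=3 | k=3, g=3 |
|---|---|---|---|---|
| Week 1 only | 0.0066 | 0.0201 | 0.0199 | 0.0603 |
| Nine days (week-2 residual variance × 7/2) | 0.0078 | 0.0236 | 0.0234 | 0.0709 |
| Never dosed, all 12 weeks (= g × k/50) | 0.020 | 0.060 | 0.060 | 0.180 |

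For scale, assume a between-subject SD of 1.5 to 2.5 HDD/week. The largest shift from the 10-day rule is then 0.0709/(0.1975 × 2.5) = 0.14 to 0.0709/(0.1975 × 1.5) = 0.24 standard errors of the interaction. The smallest, 0.0066, is 0.01 to 0.02.

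**4. Incomplete weeks**

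The response in Section 7.2 is a weekly count. A subject with 1 to 6 days has no complete week; one with 7 to 9 days has one week and a fragment. No exposure offset or partial-week rule is stated. The 10-day rule does not remove the need for one, since 10 days is one full week plus three days.

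**5. Effect on power**

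Scaling from 81% at 47 per cell, 50 per cell gives Φ(2.838 × √(50/47) − 1.960) = Φ(0.967) = 83%. Using all randomised subjects costs no planned power.

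**The case against.** The best defence is that Section 7.3 is the one section written to define the analysis population, gives exact criteria and openly says modified. A specific section normally governs general statements. The sentence in 7.2 can be read as saying only that weeks 1 to 6 and incomplete subjects stay in the model. Much of this stands: a reader might infer that nobody can tell who enters the primary test, and that goes too far, because an analyst would very likely apply 7.3. It does not rescue the text, since 3.2.1 names all randomised subjects and 7.2 claims intent-to-treat without qualification.

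A second objection is that a mixed model for weekly counts does not simply accept 1 to 9 days of data without a partial-week rule. That is right, and the fix must supply one.

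A third is that very few subjects would be touched. Under Section 6.3 the first medication is given on the baseline day, and missing TLFB is sought after withdrawal. Subjects with fewer than 10 days have no data in weeks 7-12 and act on the contrast only through the shared time trend and random intercept. The 0.18 figure needs three never-dosed, fully followed subjects in one cell, each 3 HDD/week apart, and nothing in the documents suggests that. This also stands, and it limits the weight of the point.

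Finally, aligning 3.2.1 and 7.2 to the modified set and adding an all-randomised sensitivity analysis would also remove the contradiction. It would, but it would leave the post-randomisation exclusion in the primary analysis.

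**Conclusion.** The contradiction is certain; its numerical effect is probably small and cannot be determined from the documents. The illustrative range of 0.007 to 0.071 HDD/week for the 10-day rule rests on assumed counts, assumed constant gaps, a single affected cell and a linear approximation.

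A reader might go further and infer that the exclusion biases the comparison, for instance through early adverse effects on topiramate. The 10-day condition could depend on arm, but the documents do not show that it will. Capsules match and staff are blinded (Sections 5.4 and 5.8), so the one-dose condition has no evident route to depend on arm. In the investigators' previous 200 mg/day trial, completion was 83.6% on topiramate and 85.9% on placebo (Section 1.4), with no differential attrition reported (Section 1.5).

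The point is therefore an internal inconsistency about the primary analysis set, minor to should-fix.

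**What to change.** - **Section 7.3:** define the primary efficacy set as all randomised subjects with any post-randomisation TLFB data, analysed as assigned, including days recalled after withdrawal.
- **Section 7.2:** state how incomplete weeks enter the model, either with an offset for log(days observed in the week) or by modelling heavy drinking days out of days observed.
- **Sensitivity analysis:** keep the one-dose, 10-day set in this role.
- **Wording:** make 3.2.1, 7.2 and 7.3 describe the same primary set. Optionally, report exclusions by the four medication by genotype cells.

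The cost is one paragraph in 7.3, a sentence or two in 7.2 and matching wording in 3.2.1, with no new data collection. The downside is that a few subjects with little data enter the model and the partial-week offset has to be specified. The change is best made before the blind is broken, which Section 5.8 places after database lock.

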7.4 Genetic Analyses

Genotyping will be performed by [name] in the Department of Psychiatry at the University of Pennsylvania Perelman School of Medicine. Whole blood will be coded and shipped to [name] lab. Samples will be hand-delivered or transported via courier without identifiers, following University of Pennsylvania shipping procedures. Staff will send the blood sample after collection at screening visits. Staff will keep a log of all samples sent to [name] lab, maintaining tracking logs of all samples sent verified with results received within 5 days to determine inclusion criteria. DNA will be purified from whole blood standard methods. TaqMan allelic discrimination assays will be used to genotype rs2832407 using kits provided by Applied Biosystems Inc. Genotyping will be performed using the 5'-nuclease TaqMan closed-tube fluorescence method and an ABI Sequence Detector System for post-PCR plate reads. [name] lab will send genotype information to study staff designated as the randomization staff member who is not otherwise involved in the conduct of the study. That individual will maintain a log of all subjects' genotype results and inform study staff if the subject is eligible for randomization to study medication due to genotype, keeping the study staff member blinded to the subject's genotype.

If necessary to ensure the timeliness of the genotyping, we will send a blood sample to the University of Pennsylvania's Molecular Profiling Facility as an alternative to [name] laboratory. Under those circumstances, procedures similar to those described above will be used to ensure privacy and maintenance of the blind.

8 Safety and Adverse Events

8.1 Definitions

Unanticipated Problems Involving Risk to Subjects or Others

Any incident, experience, or outcome that meets all of the following criteria:

- Unexpected in nature, severity, or frequency (i.e. not described in study-related documents such as the IRB-approved protocol or consent form, the investigators brochure, etc.)
- Related or possibly related to participation in the research (i.e. possibly related means there is a reasonable possibility that the incident experience, or outcome may have been caused by the procedures involved in the research)
- Suggests that the research places subjects or others at greater risk of harm (including physical, psychological, economic, or social harm).

Adverse Event

CONFIDENTIAL

This material is the property of the University of Pennsylvania. Do not disclose or use except as authorized in writing by the study sponsor

An **adverse event** (AE) is any symptom, sign, illness or experience that develops or worsens in severity during the course of the study. Intercurrent illnesses or injuries should be regarded as adverse events. Abnormal results of diagnostic procedures are considered to be adverse events if the abnormality:

- results in study withdrawal
- is associated with a serious adverse event
- is associated with clinical signs or symptoms
- leads to additional treatment or to further diagnostic tests
- is considered by the investigator to be of clinical significance

Serious Adverse Event

Adverse events are classified as serious or non-serious. A **serious adverse event** is any AE that is:

- fatal
- life-threatening
- requires or prolongs hospital stay
- results in persistent or significant disability or incapacity
- a congenital anomaly or birth defect
- an important medical event

Important medical events are those that may not be immediately life threatening, but are clearly of major clinical significance. They may jeopardize the subject, and may require intervention to prevent one of the other serious outcomes noted above. For example, drug overdose or abuse, a seizure that did not result in in-patient hospitalization, or intensive treatment of bronchospasm in an emergency department would typically be considered serious.

All adverse events that do not meet any of the criteria for serious should be regarded as **non-serious adverse events**.

Adverse Event Reporting Period

The study period during which adverse events must be reported is normally defined as the period from the initiation of any study procedures to the end of the study treatment follow-up. For this study, the study treatment follow-up is defined as 30 days following the last administration of study treatment.

Pre-existing Condition

A preexisting condition is one that is present at the start of the study. A preexisting condition should be recorded as an adverse event if the frequency, intensity, or the character of the condition worsens during the study period.

General Physical Examination Findings

At screening, any clinically significant abnormality should be recorded as a preexisting condition. At the end of the study, any new clinically significant findings/abnormalities that meet the definition of an adverse event must also be recorded and documented as an adverse event.

Post-study Adverse Event

All unresolved adverse events should be followed by the investigator until the events are resolved, the subject is lost to follow-up, or the adverse event is otherwise explained. At the last scheduled visit, the investigator should instruct each subject to report any subsequent event(s) that the subject, or the subject's personal physician, believes might reasonably be related to participation in this study. The investigator should notify the study sponsor of any death or

CONFIDENTIAL

adverse event occurring at any time after a subject has discontinued or terminated study participation that may reasonably be related to this study. The sponsor should also be notified if the investigator should become aware of the development of cancer or of a congenital anomaly in a subsequently conceived offspring of a subject that has participated in this study.

Abnormal Laboratory Values

A clinical laboratory abnormality should be documented as an adverse event if any one of the following conditions is met:

- The laboratory abnormality is not otherwise refuted by a repeat test to confirm the abnormality
- The abnormality suggests a disease and/or organ toxicity
- The abnormality is of a degree that requires active management; e.g. change of dose, discontinuation of the drug, more frequent follow-up assessments, further diagnostic investigation, etc.

Hospitalization, Prolonged Hospitalization or Surgery

Any adverse event that results in hospitalization or prolonged hospitalization should be documented and reported as a serious adverse event unless specifically instructed otherwise in this protocol. Any condition responsible for surgery should be documented as an adverse event if the condition meets the criteria for an adverse event.

Neither the condition, hospitalization, prolonged hospitalization, nor surgery are reported as an adverse event in the following circumstances:

- Hospitalization or prolonged hospitalization for diagnostic or elective surgical procedures for a preexisting condition. Surgery should **not** be reported as an outcome of an adverse event if the purpose of the surgery was elective or diagnostic and the outcome was uneventful.
- Hospitalization or prolonged hospitalization required to allow efficacy measurement for the study.
- Hospitalization or prolonged hospitalization for therapy of the target disease of the study, unless it is a worsening or increase in frequency of hospital admissions as judged by the clinical investigator.

